10.4 Safety Reports

The EBMT CTO will submit yearly DSUR to applicable Ethics Committees and Regulatory Authorities. This will commence one year from the date of first Regulatory Authority approval in the first country authorised.

10.6 Pregnancy Reporting and Follow-up

Any pregnancy occurring during the trial must be reported to the EBMT CTO using the pregnancy report (and by the EBMT CTO to Novartis and Pfizer, as agreed in the contract); any pregnancy will be followed up until 6 weeks after patient or patient partner gives birth.

11. End of Trial

It is planned that the trial will be completed after the last patient last follow-up, i.e. after the last recruited patient has completed 2 years of follow-up from treatment start.

11.1 Early termination of the trial

The trial may be prematurely terminated, if in the opinion of the steering committee and/or the IDMC, there is sufficient reasonable cause. Written notification documenting the reason for trial termination will be provided to the investigator by the terminating party.

Circumstances that may warrant termination include, but are not limited to:

- Determination of unexpected, significant, or unacceptable risk to patients.
- Failure to recruit patients at an acceptable rate.
- Insufficient adherence to protocol requirements.
- Insufficient complete and/or evaluable data.
- Plans to modify, suspend or discontinue the development of the IMP.
- Emerging unacceptable safety profile as determined by the IDMC
- Other trial specific stopping rules: none

12. Statistics Methodology

12.1 Sample Size Justification

This is a superiority study aiming to increase the 3-months complete response (CR) rate. CR rate after standard immunosuppression with hATG+CsA is estimated to be below 10%, and equal to 7% in a recent study from the NIH[17]. The sample size is calculated on the hypothesis that the experimental arm will increase the 3-months response rate up to 21% (by 3 folds, based on the 7% reported in Scheinberg et al [17]). In these conditions, the sample size to reject the null hypothesis at 5% significance level and with 80% power (two-sided test) is n=96 patients for each treatment arm (in total 192 patients). Calculations are based on the Pass2000 algorithm for differences of percentages in two independent samples. The sample size will be increased by 4% to compensate for possibly not evaluable patients for a total number of 200 patients to be enrolled (100 each treatment arm).

12.2 Randomisation and Stratification

Randomisation will take place on the day or day before hATG is started. Randomisation ratio will be 1:1. Randomisation will follow a stratified variable-length block design. Stratification will be done according to center size, patient's age and disease severity to ensure homogeneity between treatment arms, according to the following subgroups:

Center size:

- Each center with expected accrual ≥ 20 patients: one stratum
- All centers with expected accrual < 20 patients: lumped together in one stratum

Disease severity:

- Severe aplastic anemia (SAA)
- Very severe aplastic anemia (VSAA: SAA plus ANC $< 200/\mu\text{L}$)

Age:

- ≥ 15 and < 40 year old
- ≥ 40 year old

12.3 Statistical Methods

The primary analysis will evaluate the complete response rate at 3 months from randomisation in an ITT population containing all randomized patients. Response is defined in section 9.6.1. We expect a very limited number of cases alive at 3 months and non-evaluable, or withdrawals before 3 months; these cases will be excluded from the primary analysis, and sensitivity analyses will be performed to check the validity of conclusions.

The null hypothesis of no difference in CR rate at 3 months between the arms will be tested against the alternative of a difference in CR rate by assessing the Mantel Haenszel pooled Odds Ratio for arm yielded by a model stratified for center, age and disease severity (strata defined in 7.1 and 12.2; alpha level of .05).

The analysis of survival-like endpoints (OS, EFS; defined in 9.6) will be done by Kaplan-Meier curves and stratified Log-Rank test and Cox regression (provided the absence of relevant deviations from the assumption of proportionality of hazards).

The analysis of time-to-event endpoints with competing risks (Time to first response, Time to best response, Time to CR, RI, Clonal evolution, PNH and immunosuppression discontinuation; defined in 9.6) will be done by crude cumulative incidence curves, Gray test, and Cox regression for cause-specific hazards (provided the absence of relevant deviations from the assumption of proportionality).

Other secondary endpoints (CsA-independent hematological response at 24 months, Need for transfusions, Need for any supportive care including hospitalization, Safety and tolerability) will be described by standard summary statistics (frequency tables for categorical variables, mean with standard deviations and quantiles for continuous variables).

QoL data will be analyzed by mixed models, assessing changes over time and differences between treatment arms.

Exploratory analyses of outcomes will also address the impact of other relevant predictive factors, which include:

- The presence of a PNH population
- The presence of HLA dr 15
- Pre-treatment absolute reticulocyte count
- Pre-treatment absolute lymphocyte count
- ANC at 1 month (time-dependent covariate)
- Platelets and absolute reticulocyte count at 3 months (time-dependent covariate)

For all tests, the alpha level will be .05. All analyses will be performed in SPSS and / or R.

Further details will be specified in a separate Statistical Analysis Plan (SAP).

12.4 Interim Analysis

Not planned.

12.5 Procedures for reporting Deviations to Original Statistical Analysis Plan

If agreement has been reached between the coordinating investigator(s), the statistician and the trial steering committee to deviate or make amendments to the SAP, this will be reported (i.e. explained) in the clinical study report at the end of the trial.

12.6 The selection of patients to be included in the analysis

All efficacy analyses will be based on the intention-to-treat principle, including all patients randomized and comparing groups based on the arm assigned at randomisation. In the unlikely case of patients found to be not eligible after randomisation or going off-study before receiving the treatment, these cases would be excluded, and secondary analyses will be performed to check the sensitivity of conclusions when these cases are included.

As specified in 9.6.1 and 12.3, the analysis of the primary endpoint will include all cases evaluable at 3 months, considering death before 3 months as a failure to achieve CR. Patients alive at 3 months and non-evaluable or withdrawals before 3 months will be excluded from the primary analysis, and sensitivity analyses will be performed to check the validity of

conclusions. The scenarios will be : i) all cases failures ; ii) all cases CR ; iii) all experimental arm cases failures, all control arm cases CR.

The safety analyses will be performed on the subpopulation of cases who started the treatment.

13. Data Management

The EBMT software in use at time of the beginning of the trial will be adopted for this study.

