9.6 Statistical criteria and definition of endpoints

9.6.1 Response rate (main endpoint)

The primary analysis will evaluate complete response rate at 3 months from randomisation in an intent-to-treat (ITT) population containing all randomized patients. A valid response has to be measured at month 3 plus and minus 10 days; in case of more than one measurement in this period, the best response will be taken. Death before 3 months will be considered a failure (i.e. no response). We expect a very limited number of cases alive at 3 months and non-evaluable, or withdrawals before 3 months; these cases will be excluded from the primary analysis, and sensitivity analyses will be performed to check the validity of conclusions.

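### The primary analysis is labelled intention-to-treat in all randomised patients, but its exclusion rules make it an evaluable-case analysis

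*Protocol*

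**What the plan says.** Three places declare the full randomised population. Section 9.6.1 sets the primary analysis "in an intent-to-treat (ITT) population containing all randomized patients". Section 12.3 says: "The primary analysis will evaluate the complete response rate at 3 months from randomisation in an ITT population containing all randomized patients". Section 12.6 opens with: "All efficacy analyses will be based on the intention-to-treat principle, including all patients randomized and comparing groups based on the arm assigned at randomisation".

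The exclusions follow in the same sections.

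- **Non-evaluable at 3 months, or withdrawn before 3 months.** Section 9.6.1 says "these cases will be excluded from the primary analysis, and sensitivity analyses will be performed to check the validity of conclusions". Section 12.3 repeats this, and 12.6 has it as "Patients alive at 3 months and non-evaluable or withdrawals before 3 months will be excluded from the primary analysis".
- **Ineligible or never treated.** Only section 12.6 adds this: "In the unlikely case of patients found to be not eligible after randomisation or going off-study before receiving the treatment, these cases would be excluded".

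Some patients are kept. Death before 3 months counts as failure (9.6.1, 12.6). Section 6.3 keeps a patient who is taken off treatment in the trial and its follow-up unless consent is withdrawn.

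Section 12.6 fixes three scenarios for the first group: (i) all failures, (ii) all CR, (iii) experimental-arm cases failures and control-arm cases CR. For the second group it promises that "secondary analyses will be performed to check the sensitivity of conclusions when these cases are included", with no rule for the outcome to assign. The synopsis describes the trial as open label.

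**The concern.** The declared population and the exclusions cannot both hold. A set that omits withdrawn, non-evaluable, ineligible and untreated patients does not contain everyone randomised. This is not detail left to a SAP, because the protocol itself fixes the rule.

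Staff and patients know the allocation. Withdrawal from the trial, attendance in the month-3 window and a later judgement of ineligibility can therefore all depend on arm. Removing a patient who did not reach CR raises the observed CR rate of that arm, so unequal removal shifts the comparison. The phrase about going off-study before treatment adds an uncertainty: section 7.2.1 starts ATGAM and cyclosporine on day 1 but eltrombopag on day 14. If the phrase means the full assigned regimen, the rule would reach further in one arm than in the other.

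At stake is whether the confirmatory test has the protection of randomisation that its label promises.

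**Working it through.** **Inputs.** From section 12.1: CR 7% v 21%, two-sided alpha 0.05, power 80%, 96 per arm raised by 4% to 100. Assumed, because the protocol gives only the 4%: how losses split between arms, that all those lost are non-responders, and a true CR rate of 10% in both arms for the error rates. Losses are written control v eltrombopag. Tests are unstratified chi-square without continuity correction; the planned test is a stratified Mantel-Haenszel odds ratio.

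**1. The plan's sample size.** With mean rate 0.14:

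n = [1.96·√(2·0.14·0.86) + 0.842·√(0.07·0.93 + 0.21·0.79)]² / 0.14² = (0.962 + 0.405)² / 0.0196 ≈ 95.2, so 96 per arm.

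96 / 0.96 = 100. Both figures reproduce.

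**2. Direction of the bias.** With x responders among n randomised and k non-responders removed, the observed rate is x/(n−k). At 10/100 in both arms:

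- 4 v 4: 10/96 in each arm, difference 0.
- 0 v 4: 10/96 − 10/100 = 10.4% − 10.0% = +0.4 points.
- 2 v 10: 10/90 − 10/98 = 11.1% − 10.2% = +0.9 points.

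**3. Error rate.** Exact binomial enumeration, 100 randomised per arm, true CR 10% in both:

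| Lost (control v eltrombopag) | Rejects in favour of eltrombopag | Two-sided |
|---|---|---|
| none | 2.6% | 5.2% |
| 4 v 4 | 2.6% | 5.2% |
| 0 v 4 | 3.3% | 5.4% |
| 2 v 10 | 4.2% | 5.8% |

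**4. A borderline result.** Take eltrombopag 17/100 and control 8/100.

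- All randomised: pooled rate 25/200 = 0.125; z = 0.09 / √(0.125·0.875·0.02) = 1.92; p = 0.054.
- 4 v 4 lost: 17/96 v 8/96, p = 0.054.
- 2 v 10 lost: 17/90 v 8/98; pooled 25/188 = 0.133; z = 0.107 / 0.0496 = 2.16; p = 0.030.
- Reversed, 10 v 2 lost: 17/98 v 8/90; z = 0.0846 / 0.0496 = 1.71; p = 0.088.

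**5. The scenarios.** At the planned effect with 4 lost per arm, the evaluable-case test (20/96 v 7/96) gives p = 0.007. Scenario i (20/100 v 7/100) gives 0.007, ii (24/100 v 11/100) gives 0.016 and iii (20/100 v 11/100) gives 0.079. The protocol does not say what follows when they disagree.

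**6. Power after the change.** With 4% counted as no CR, the rates become 0.07·0.96 = 6.7% and 0.21·0.96 = 20.2%. Exact power with 100 per arm is 82.0%, against 82.1% with 96 evaluable per arm. By the normal approximation it is 80.0% against 80.3%. At 10% missing the approximation gives 77.0% against 77.7%.

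**The case against.** A reader might infer that this is a completer analysis, or that anyone who leaves for toxicity or another treatment is deleted. The documents do not support either reading. Deaths are failures. Under section 6.3 a patient who stops treatment stays in follow-up and is analysed if assessed in the month-3 window. What is lost is trial withdrawal, no valid month-3 assessment, ineligibility and never being treated.

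The sponsor can also say that such cases are expected to be few, with an allowance of 4%. The bounding scenarios are fixed in advance, and scenario iii is harsher on eltrombopag than the proposed primary analysis. The 2 v 10 split is an assumption chosen to show the mechanism. The direction is not given either, since heavier control loss would work against eltrombopag.

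All of this stands and limits the size of the problem. It does not remove the contradiction. The scenarios would show that a result is fragile, but they do not change which test decides the trial. They are also listed only for withdrawn and non-evaluable patients.

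**Conclusion.** The point holds as a mismatch between the declared and the actual primary population. The analysis is an evaluable-case one and should not be called intention-to-treat.

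The likely numerical effect is modest: none when equal numbers of non-responders are lost, and small if the protocol's 4% falls wholly on the eltrombopag arm. It becomes material only with clearly unequal loss. A claim that the type I error is seriously inflated would go too far, since even 2 v 10 moves the two-sided rate only from 5.2% to 5.8%. The one-sided shift and the possible change of a borderline p-value are the more relevant risks.

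These sizes rest on the assumed splits, on all lost patients being non-responders, on a true CR rate of 10% for the error rates, and on an unstratified test. The contradiction in the text rests on none of them.

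**What to change.** In 9.6.1, 12.3 and 12.6, define the primary set as all randomised patients in their assigned arm. Count anyone without a documented CR in the month-3 window as no CR, whatever the reason. This is scenario i, extended to ineligible and untreated patients; those among them with a documented CR count as CR. Delete the exclusion of these two groups from the primary set. Keep the evaluable-case analysis and scenarios ii and iii as sensitivity analyses.

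The cost is wording. CR rates read slightly lower (21% becomes about 20.2% at 4% missing). Power is essentially unchanged at 4% missing and less than one point lower at 10%, and 200 patients still suffice at the planned 4%. Counting missing as no CR is not free of bias, because it can penalise the arm with more missing data. Scenarios ii and iii help to bound that.

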13.1 Data Management Responsibility

It is the responsibility of the Principal Investigator (PI) at each site to ensure the accuracy, completeness, legibility, and timeliness of the data reported. All source documents must be completed in a timely, neat, legible manner to ensure accurate interpretation of data.

All source documents, CRFs, and laboratory reports must be reviewed by the PI's research team or Data Manager, who must ensure that they are accurate and complete before submitting CRFs to the CTO. Adverse events must be graded, assessed for severity and causality, and reviewed, dated and signed by the site PI or Co-Investigator (see section 11.2). All laboratory reports must be reviewed, dated and signed by the site PI or Co-Investigator.

13.2 Data Capture

Data for this trial will be captured in paper CRFs. CRFs must be completed in dark ink i.e. blue or black as this will ensure reproduced copies are clear.

All data requested on the CRFs must be recorded, and any missing data must be explained.

In an event where an entry error has occurred, correction must be made by crossing out the original entry with a single line, and writing the initials of the person making the change and the date of the change. The new data should be entered above or next to the strike-through. The original data must not be erased, overwritten and correction fluid/tape must not be used.

13.3 Definition of Source Data for the trial

The data that is reported on the CRFs is the source for EBMT. Sites need to retain a copy of the CRF and should retain all of the patient notes, lab results, etc. as that is their source.

14. Ethics and Regulatory Approvals

14.1 Good Clinical Practice (GCP)

The trial will be conducted in accordance with ICH-GCP, the Declaration of Helsinki, and the appropriate local regulatory requirements. Essential clinical documents will be collected and maintained by the EBMT CTO to demonstrate the validity of the trial and the integrity of the data collected.

The sponsor's Trial Master File (TMF) will be maintained at the EBMT CTO. Each participating site will maintain an investigator site file (ISF) as per the EBMT Clinical Trials Manual provided by the CTO. This sponsor's TMF and the ISF should be established at the beginning of the trial, maintained for the duration of the trial and retained according to the appropriate regulations.

The EBMT Clinical Trials Manual provides further guidance on the conduct of the trial.

14.2 Ethical and Regulatory Considerations

The ethics committee(s) and the appropriate regulatory authority(ies) will review all appropriate trial documentation in order to safeguard the rights, safety and well being of the patients. The trial will only be conducted at sites where ethics and regulatory approval has been obtained. The PI, EBMT CTO or CRO will provide the relevant ethics committee(s) and the regulatory authority(ies) with the final version of the protocol, patient information and informed consent form (ICF), any other written information given to patients, safety updates, annual progress reports, and any revisions to the trial protocol or any other required trial documentation.

This study is registered at on clinicaltrials.gov with the number NCT02099747.

14.3 Patient Information & Consent (appendix 7)

A generic patient information leaflet (PIL)/ Informed Consent Form (ICF) is provided in English in the Appendix of the protocol. This is a sample and should be amended as required to meet local requirements and will be translated into local language as necessary. Local versions should be appropriately version controlled, clearly stating whether it is country or site specific in the footer and dated to reflect the protocol with which it is associated. A copy of the local version must be provided to the CTO.

The method of obtaining and documenting the informed consent and the contents of the consent will comply with ICH-GCP and all applicable regulatory requirement(s) and must be approved by the Ethics Committee prior to use:

For patients who are 18+:

- A properly signed and personally dated informed consent form is required for each patient before any trial specific procedure. After the trial has been fully explained the patient should be given ample time to read the patient information sheet and consent form and ask questions. Written informed consent will always be obtained from the patient and/or his/her guardian or legal representative prior to trial participation.
- The informed consent process should be recorded in source documents (date of information and consent, parties present).
- The investigator is responsible for checking entries, and initials made by the patient on the consent form, and to request correction immediately in case of missing, illegible or incorrect dates. The person taking the patient consent should sign and date both consent forms to confirm he/she provided information to the patient.
- All entries on the consent forms must be permanent (no pencil).
- The Informed Consent form will be updated by the Investigator-Sponsor whenever important new information becomes available that may be relevant to patient's consent. This may be a result of amendments to the protocol, new information regarding the trial medication or alternative treatments. Revised versions must be approved by the relevant ethics committee(s) and regulatory authority(ies) before use.
- The revised consent form must be signed by patients who are entered in the trial and who have not yet completed trial treatment. In particular, if the consent form is updated with new safety information, a new version of the informed consent form must be provided to all patients in the trial in a timely manner as soon as written ethics and regulatory authority(ies) approval is obtained.
- Patient withdrawal of consent from the trial should be explicitly documented in the source documents and notified to the CTO via the early termination CRF.

For patients who are 15-18 years of age:

- A properly signed and personally dated informed consent form is required for each patient before any trial specific procedure. The informed consent of the parents or legal representative is required; consent must represent the minor's presumed will and maybe revoked at any time, without detriment to the minor;
- The minor is given information according to its capacity of understanding, from staff with experience with minors, regarding the trial, the risks and the benefits
- Minors who are capable of forming an opinion, assessing and understanding the purpose of the study and can assess its consequences need to be informed directly by their physicians and will receive an age appropriate information form. Their agreement with the study needs to be indicated with a signature on the consent form.
- After the study has been fully explained to the minor and to their parents/legal guardians, ample time must be given to read the consent forms and ask questions.
- The informed consent process should be recorded in source documents (date of information and consent, parties present).
- The investigator is responsible for checking entries made by the minor and parents/legal guardians on the consent form, and to request correction immediately in case of missing, illegible or incorrect dates. The person taking the patient consent

should sign and date both consent forms to confirm he/she provided information to the patient and to parents/legal guardian.

- All entries on the consent forms must be permanent (no pencil).
- The Informed Consent form will be updated by the Investigator-Sponsor whenever important new information becomes available that may be relevant to subject's consent. This may be a result of amendments to the protocol, new information regarding the trial medication alternative treatments. Revised versions must be approved by the relevant ethics committee(s) and regulatory authority(ies).
- Patient withdrawal of consent from the study should be explicitly documented in the source documents and notified to the CTO via the early termination CRF.

